### 3.1.7 Reference start date

The reference start date is defined as the date of the first dose of investigational product.

- If the date of the assessment/event is on or after the reference date, then:  
Relative study day = (date of event – reference date) + 1
- If the date of the assessment/event is prior to the reference date, then:  
Relative study day = (date of event – reference date)

In the situation where the assessment/event date is partial or missing, relative study day and corresponding durations will appear partial or missing in the data listings.

### 3.1.8 Analysis visits – Retests and Unscheduled Assessments

By-visit summaries will be presented by scheduled electronic case report form (eCRF) visit in form of a Day and a Week with a corresponding timepoint where applicable, unless otherwise specified. No analysis visit windowing will be applied unless otherwise specified.

If more than one assessment coincides with the date of the scheduled visit as per the eCRF visit form, then the following will apply:

- If assessment is associated with a scheduled timepoint as per the protocol, then such assessment will be used for analysis.
- If more than one assessment per specific visit is associated with a scheduled timepoint as per the protocol, then the latest assessment according to the assessment date/time with non-missing result will be used for analysis.
- If for such assessments a timepoint is not defined in the protocol, then the latest assessment according to the assessment date/time with non-missing result will be used for analysis.

In addition, due to the extension of the follow-up period as per the protocol amendment 2 dated 14OCT21, certain assessments were performed only during the Week 32 as supposed to Week 28 as done in the previous versions of the protocol. Provided that no windowing is applied some of such assessments will be mapped to Week 28 and some to Week 32 depending on at what visit the assessment was actually performed as per the eCRF visit form. Consequently, the by-visit summaries will include both visits.

**NRS daily scores** and **DSIS** will be mapped so that all assessments prior to Day 1 visit will be mapped to screening, the NRS daily score which date coincides with the Day 1 visit will be

mapped to that visit (Day 1) as well as all subsequently recorded scores (scheduled/unscheduled) up to but NOT including the NRS daily score that coincides with Week 1 visit date as recorded on the eCRF. This score will be mapped to Week 1 visit. The same logic will be applicable for the remaining visits and recorded daily scores. Only those averages associated with the protocol defined visits will be used for analysis and summaries.

**All secondary endpoints,** CCI [REDACTED] and TNSn will be mapped based on their date of assessment that coincides with the date of the visit (including unscheduled visits) as per the eCRF. The exception will be assessments prior to the first IP administration that will be automatically mapped to screening or rescreening visit depending on the assessment dates. Only those assessments associated with the protocol defined visits will be used for analysis and summaries.

**ABPM assessments** will be mapped only to two visits with labels: “Screening” and “Day 70, Week 10”. If more than one assessment is available, then:

- Screening: baseline will be determined as per section 3.1.2 and remaining assessments will be mapped to screening;
- Post-baseline: the last recorded assessment will be used for analyses.

X-rays and MRI will be mapped only to two visits with labels: “Screening” and “Day 224, Week 32”. If more than one assessment is available, then:

- Screening: baseline will be determined as per section 3.1.2 and remaining assessments will be mapped to screening;
- Post-baseline: the last recorded assessment will be used for analyses.

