### **3.1.4 Early termination visit**

Assessments associated with an early termination of IP are the same as those for EOT (Week 12) visit. Consequently, summaries presented by visit will not differentiate whether the Week 12 assessments correspond to the EOT or the ET visit. The exceptions are the primary endpoint, secondary endpoints, **CCI**, TNSn and DSIS for which the handling of the data associated with ET visit can be found in sections 3.2, 3.3, 3.6.4 and 3.5.1.1 respectively.

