### **3.2 Primary efficacy variables**

The primary efficacy variable is the change in weekly average of daily NRS pain scores from baseline to Week 12.

The NRS is an 11-point Likert scale used to assess pain, where participants are asked to describe their average pain in the target knee by identifying a number from 0 = “no pain” to 10 = “most severe pain imaginable over the previous 24 hours”. This will be recorded on a daily basis at approximately the same time every morning. The daily NRS pain scores will be recorded via electronic patient recorded outcome (ePRO) diary.

The relevant visit associated with the daily NRS scores will be derived based on the date of NRS pain scores that coincide with the relevant visit date as recorded on the electronic case report form (eCRF). Therefore, the Week 12 weekly average of daily NRS pain scores is the average of the daily NRS pain scores of 7 days up to and including the date on which the week 12 (EOT/ET) visit occurred.

For participants that discontinue the treatment period, the date of the ET visit as recorded on the eCRF in form of the week 12 (EOT/ET) visit will be associated with the protocol defined visit based on the study day, and the 7-day average for that specific visit will be derived using the same approach as described above for the Week 12 average. If the ET visit coincides with the target study day of the EOT visit, then this ET average will not be derived as it cannot represent a valid Week 12 average. In other words, only participants that complete the treatment will have Week 12 average derived. For those who prematurely withdraw from the treatment the Week 12 average will be imputed. At least four of the seven daily scores need to be recorded by the participant to obtain a weekly average value including baseline for the statistical analyses.

If there are less than four daily scores for the Week 12 average due to an inappropriate visiting schedule of Week 11 (Week 11 and Week 12 in close succession), the derivation of the Week 12 average will take priority over the Week 11 average. The weekly average will be derived in the same manner as described above but daily scores that may have been used for derivation of the Week 11 average would instead be used for derivation of the Week 12 average to ensure that at least 4 scores are available.

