### **3.6.4 Total neuropathy score- nurse (TNSn) variables**

The total neuropathy score – nurse (TNSn) assessment is collected as scores as follows:

- Sensory symptom score
  - Sensory symptoms consist of six questions, each rated from 0 to 4.
  - Sensory symptom score is determined as the maximum of the six scores.
- Motor symptom score
  - Motor symptoms consist of four questions, each rated from 0 to 4.
  - Motor symptom score is determined as the maximum of the four scores.
- Autonomic symptom score
  - Autonomic symptoms consist of six symptoms rated as present or not (yes/no)
  - Autonomic symptom score is determined as the number of symptoms present, with a maximum score of 4 assigned for four or more symptoms present.
- Pin sensibility score
  - Pin sensibility is scored as 0 to 4 in upper and lower limbs both left and right, therefore four areas in total.
  - Pin sensibility score is determined as the maximum of the four scores.
- Vibration sensibility score
  - Vibration sensibility is scored as 0 to 4 in upper and lower limbs both left and right, therefore four areas in total.
  - Vibration sensibility score is determined as the maximum of the four scores.
- TNSn total
  - The total score is determined as the sum of the five aforementioned scores.

The TNSn assessment will be performed during screening, treatment period and follow-up period, as indicated in CSP (Table 1).

The ET assessments will be handled in the same manner as for primary endpoint that is will be reassigned based on the study day.

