#### **4.2.6.9 Total neuropathy score-nurse (TNSn) results**

A summary of the total neuropathy score – nurse (TNSn) results will be prepared, including results for each of the following categories:

- Sensory symptom score
- Motor symptom score
- Autonomic symptom score
- Pin sensibility score
- Vibration sensibility score
- TNSn total

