- Provided that the ECG evaluations are performed locally by sites, only the abnormal evaluations will be listed.
- Given that TNSn and Injection site reactions data are tabulated, the listings were not generated.

- An additional AESI category was defined in this SAP that does not feature in the protocol. This category was classed as ‘Other AESIs’ and has been defined as any other AEs that are deemed of an interest by the study team.

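### TNSn scores taken after dosing at unscheduled visits appear in no planned TNSn output, and the rule for early-termination TNSn scores on the Week 12 target day is unclear

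*SAP*

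**What the plan says.** SAP section 3.1.8 groups TNSn with the secondary endpoints for visit mapping. It says that "TNSn will be mapped based on their date of assessment that coincides with the date of the visit (including unscheduled visits" as recorded on the eCRF), and makes one exception: "The exception will be assessments prior to the first IP administration that will be automatically mapped to screening or rescreening visit". It then limits what is used: "Only those assessments associated with the protocol defined visits will be used for analysis and summaries".

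Section 4.2.6.9 plans a single TNSn output, a summary of five component scores and the total. It names no worst-value or any-time row. Section 6 removes the listing: "Given that TNSn and Injection site reactions data are tabulated, the listings were not generated".

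For early termination, the general rule in section 3.1.4 is that "summaries presented by visit will not differentiate whether the Week 12 assessments correspond to the EOT or the ET visit", but TNSn is one of the named exceptions. Section 3.6.4 gives the TNSn rule: "The ET assessments will be handled in the same manner as for primary endpoint that is will be reassigned based on the study day". The primary-endpoint rule it points to, in section 3.2, reassigns an ET visit by study day and adds: "If the ET visit coincides with the target study day of the EOT visit, then this ET average will not be derived". The reason given there is that such an average is not a valid Week 12 value.

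**The concern.** The reason for dropping the listing is that the table already shows the data. That holds only for scores that reach the table, and the mapping rule keeps some of them out. A safety score that is collected, mapped to an unscheduled visit and then shown in neither a table nor a listing cannot be seen by anyone reading the planned TNSn outputs.

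The ET rule raises a second problem. Section 3.2 withholds a Week 12 average from a participant who stopped treatment because of how the efficacy estimand is defined, and the Week 12 value is then imputed. That reasoning does not fit a safety score. Under section 3.1.1 variables other than the primary and key secondary ones use available data only, so nothing would replace a TNSn value dropped in this way. TNSn is also the only scored neuropathy instrument that the SAP describes during treatment: under section 3.6.6 the Survey of Autonomic Symptoms is done only at Day 1 and Week 36.

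**Working it through.** The point turns on the rules rather than on a calculation, so each kind of TNSn record is traced through them.

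| TNSn record | Governing text | In the 4.2.6.9 summary? | In a TNSn listing? |
|---|---|---|---|
| Before first dose, unscheduled | 3.1.8 exception | Mapped to screening or rescreening, so not lost by the visit rule | No (section 6) |
| Extra score on a scheduled visit date | 3.1.8, several assessments on one visit date | May be the value used | No |
| After dosing, dated only to an unscheduled visit | 3.1.8 restriction to protocol-defined visits | No | No |
| ET, away from the EOT target day | 3.6.4 and 3.2, reassigned by study day | Yes, if the day falls on a visit that is protocol-defined for TNSn | No |
| ET, on the EOT target day | 3.6.4 and 3.2 | No if the 3.2 rule carries over in full; yes if only reassignment applies | No |

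The third row is certain on the text. The fifth depends on the reading:

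1. *Full carry-over.* Section 3.1.4 takes TNSn out of the pooling of EOT and ET at Week 12, and section 3.6.4 says to proceed as for the primary endpoint. The 3.2 rule for an ET visit on the target day then applies, and the score is dropped.
2. *Reassignment only.* Section 3.6.4 explains its own cross-reference as reassignment by study day and mentions no deletion. The 3.2 exclusion is worded for a seven-day diary average, and TNSn has no such average. The score then stays at Week 12.

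Two programmers could each defend one of these.

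Other safety data in the same SAP have a safeguard that TNSn lacks:

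- Laboratory (4.2.6.4): shift tables to the on-treatment maximum or minimum, and listings that show all results of a test for any participant with an abnormal value. Liver tests (4.2.6.4.1) use scheduled and unscheduled assessments.
- Vital signs (4.2.6.5): shifts to the minimum or maximum during treatment, and a listing of confirmed or symptomatic orthostatic hypotension with all results.
- ECG (4.2.6.6): all results listed for anyone with an abnormality.
- Physical examination (4.2.6.7): abnormal findings listed, with unscheduled visits included.

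**The case against.** The case on the other side has real weight.

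- **By-visit summaries are meant for scheduled visits.** Section 3.1.8 sets this as the general convention, for safety as well as efficacy data. This stands: leaving unscheduled values out of by-visit statistics is not itself a fault. The gap is the absence of any listing or worst-value row to hold them.
- **Neuropathy is reported elsewhere.** Section 4.2.6.8 plans a key participant table for anyone with a neurological-examination abnormality, section 4.2.6.1 tabulates and lists adverse events, and section 4.2.6 allows further safety summaries. This also stands. A clinically evident neuropathy would probably be reported, but none of these planned outputs carries the TNSn score.
- **For-cause TNSn is not in the document.** A reader might infer that unscheduled scores are taken because neuropathy is suspected, so that the summary hides the worst values and understates a dose-related signal. The SAP does not say this. Section 3.6.4 refers to the protocol schedule, and the triggered work-up in section 3.6.3 is nerve conduction studies. The inference is plausible but unsupported here.
- **The ET exclusion is not stated outright.** A reader might conclude that ET scores near Week 12 are excluded. The text does not go that far: the 3.2 rule concerns the EOT target day only, and its application to TNSn is one of two readings.
- **Safety analysis is descriptive and the listing removal is openly declared.** True, and no test or primary conclusion changes. The stated reason for the removal still does not cover the scores that the table leaves out.

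**Conclusion.** The point holds in a narrow form. TNSn scores taken after dosing and dated only to an unscheduled visit appear in no TNSn output, because sections 3.1.8, 4.2.6.9 and 6 together leave them no place. The reason given for dropping the listing is incorrect for these scores. For ET scores on the EOT target day the SAP is ambiguous, and one fair reading loses them.

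It would be too strong to say that all unscheduled TNSn scores are lost, since scores before dosing and extra scores on scheduled visit dates can be used. It would also be too strong to say that a neuropathy signal will be missed.

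The number of affected scores cannot be derived from the SAP and may be zero. For scale only, about 350 randomised participants in five equal arms gives 350/5 = 70 per arm, so each affected participant is about 1/70 = 1.4% of an arm. The conclusion assumes that some TNSn scores are collected after dosing outside scheduled visits; section 3.1.8 provides for mapping them but does not say that any exist. The point concerns completeness of safety reporting and is worth correcting because the remedy is small.

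**What to change.** 1. Reinstate a TNSn listing for participants with any post-baseline increase, showing all their scheduled, unscheduled and ET assessments. This matches how laboratory, ECG and physical-examination abnormalities are already listed. As an alternative or an addition, add to section 4.2.6.9 a worst post-baseline TNSn total that uses all assessments after dosing. Correct the rationale in section 6 to match.
2. State in section 3.6.4 that a TNSn score from an ET visit on the EOT target day is kept and summarised, so that the non-derivation rule in section 3.2 is not applied to it.

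The by-visit summary can stay limited to scheduled visits. The cost is SAP wording and one listing or table block, programmed from data already collected.

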### **3.6.10 Radiographic (X-ray) and magnetic resonance imaging (MRI) assessments**

#### **3.6.10.1 X-ray assessments**

All participants should undergo diagnostic x-ray on the shoulder, knee, and hip joints during screening period while at Week 32 visit, x-ray imaging is performed on the knee and hip joints. Any potentially clinically significant findings detected on X-ray performed at week 32 will be further assessed and sent for adjudication. In addition, unscheduled X-ray should be performed “for cause” to follow up on any worsening symptoms. These assessments will aid

identification of joint safety events such as RPOA, SIF, primary osteonecrosis, or pathological fractures.

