#### 4.2.6.4 Laboratory results

Tables with descriptive summaries (mean, SD, median, minimum, and maximum) of actual (absolute) values and changes from baseline values will be produced for each treatment group at each visit. Tables will be produced for tests specified in section 3.6.8 except for urine drug screen, urine pregnancy test, serology, and endocrinology. Participants with abnormal results of these tests except for urine pregnancy test will be only listed including all available results.

Central laboratory reference ranges will be used for the identification of abnormalities. Shift tables will be produced for the same parameters for which summary tables will be produced with the exception of urinalysis to display low, normal, and high values.

The shift tables will present baseline and maximum/minimum on-treatment value, as applicable for each parameter and will include participants with both baseline and post-baseline data. The exception would be Haemoglobin A1c that is evaluated only at baseline and Week 32 hence this shift table will present baseline and maximum/minimum value during the study.

For urinalysis parameters collected as for example: Negative, Small, Moderate or Large, shift tables from baseline to maximum value during treatment will be provided. This will apply to bilirubin, blood, leucocytes, glucose, protein and ketones. Key participant information table listing only participants and assessments with abnormal values will be produced.

Laboratory values will also be presented as box plots, for absolute values and changes from baseline. All protocol defined visits will be summarised.

Each plot will show the following details:

- Mean (symbol within each box)
- Median (horizontal line within each box)
- Q1 and Q3 (bottom and top of each box)
- Whiskers extending to the most extreme observation within 1.5 times the interquartile range from the nearest quartile.
- Outliers outside the whiskers displayed individually.
- Reference ranges shown as dotted lines on the analysis value plots, not relevant to the change from baseline plot. If more than one reference range is available for an assessment (example: due to gender differences) then the narrowest range will be used in the graph.

The plots will be prepared for each test within the laboratory categories:

- Haematology: hemoglobin, hematocrit, RBC count, platelet count (or estimate), WBC count, WBC differential

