#### **4.2.6.12 X-ray and MRI**

Summary table suggestive of abnormal findings for each treatment group at the protocol defined visits will be produced.

All data of assessable imaging will be listed for each participant. In addition, a separate listing of participants whose data was sent for adjudication will be produced presenting the outcome of the adjudication review.

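### The last-image rule for post-baseline X-ray and MRI lets an abnormal for-cause image fall out of the by-arm imaging table, and does not say whether last is per joint or per modality

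*SAP*

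**What the plan says.** Section 3.1.8 states that "X-rays and MRI will be mapped only to two visits with labels": Screening, and Day 224 (Week 32). For participants with more than one image after baseline it gives one instruction: "the last recorded assessment will be used for analyses". It does not mention joint, side or modality.

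Section 3.6.10.1 schedules one post-baseline X-ray, at Week 32, when "x-ray imaging is performed on the knee and hip joints". It adds that "unscheduled X-ray should be performed" for cause, "to follow up on any worsening symptoms". Section 3.6.10.2 schedules knee MRI at screening only; the only MRIs it describes after that are unscheduled and for cause.

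The analysis is in section 4.2.6.12: "Summary table suggestive of abnormal findings for each treatment group at the protocol defined visits will be produced". The same section lists all assessable imaging per participant, and separately lists participants sent for adjudication with the outcome.

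For laboratory data, section 4.2.6.4 takes extremes in its shift tables: "The shift tables will present baseline and maximum/minimum on-treatment value".

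**The concern.** A last-value rule suits a measurement planned once after baseline, where a repeat usually corrects the first attempt. Section 3.1.8 gives the same rule to ambulatory blood pressure, and there it fits. For-cause joint images serve another purpose: they are taken because symptoms have worsened, and they look for events that arise between scheduled visits. A later film does not correct such an image; it is a second observation at another time.

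Section 4.2.6.12 gives the only by-arm tabulation of imaging abnormalities in the SAP. If an abnormal for-cause image can be superseded there by a later image that no longer shows the finding, the table does not answer how many participants in each arm had an abnormal image after baseline. Because everything sits under the Week 32 label, it does not cleanly answer how many had an abnormal scheduled Week 32 film either.

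**Working it through.** The SAP states no figure on this point, so there is none to reproduce. The check follows the rule through the cases that can occur.

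**Direction of the error.** Number a participant's post-baseline images 1 to K in time order, and let a_k = 1 if image k is abnormal and 0 otherwise.

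- Last-image rule: L = a_K.
- Any-abnormality rule: A = max(a_1, …, a_K).

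L ≤ A for every participant, so the last-image count in any arm is at most the any-abnormality count. The shortfall in an arm is the number of participants with some a_k = 1 for k < K and a_K = 0. With one image (K = 1) the two rules agree.

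**Cases under section 3.1.8.**

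| Images after baseline | Counted as abnormal in 4.2.6.12? |
|---|---|
| Abnormal for-cause X-ray, no later image | Yes, but under the Week 32 label whenever it was taken |
| Abnormal for-cause X-ray, Week 32 X-ray still abnormal | Yes |
| Abnormal for-cause X-ray, Week 32 X-ray no longer shows it | No |
| Abnormal for-cause MRI, later normal Week 32 X-ray | Yes if last is per modality; no if pooled |
| Abnormal for-cause MRI, later normal MRI of the same joint | No |
| Abnormal Week 32 X-ray of one joint, later normal for-cause X-ray of another | Yes if last is per joint; no if pooled |

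The third and fifth rows lose an abnormal image even on the most favourable reading (per joint and per modality). The fourth and sixth depend on a definition that the SAP does not give. The last row is possible because follow-up runs beyond the Week 32 visit: 12 weeks of treatment plus 24 of follow-up is 36 weeks. The scheduled film can therefore itself be displaced.

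**Comparison with other safety rules in the SAP.** Laboratory shift tables (4.2.6.4) use maximum or minimum on-treatment values. Vital-sign shift tables (4.2.6.5) use the minimum or maximum during treatment. The liver-test summaries (4.2.6.4.1) take scheduled and unscheduled results and use maximum values in the shift table. Imaging has no such extreme-value summary.

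**Size.** It depends on how many participants have for-cause imaging, how often those images are abnormal, and how often a later image no longer shows the finding. The SAP gives none of these, so no number or defensible range can be derived.

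**The case against.** The strongest reply is that joint safety is not judged from this table. Section 4.2.6.1 tabulates the incidence of adjudicated rapidly progressive osteoarthritis, subchondral insufficiency fracture, primary osteonecrosis and pathological fracture. It also gives joint-related events of special interest with exposure-adjusted rates. Section 4.2.6.2 summarises joint replacements, and section 4.2.6.12 lists all assessable images and all adjudicated cases. None of these carries a last-image restriction. This stands, and it limits the point to one table. A reader might infer that joint events of special interest are undercounted. The SAP does not support that: section 3.6.1.1 defines them by positive adjudication, and a later image does not remove an adjudicated event.

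A reader might also infer that for-cause findings never reach adjudication, because section 3.6.10.1 states that route explicitly only for Week 32 X-rays. The route for other images may well be in the protocol, which is not shown, so nothing can be concluded from its absence here.

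A third tempting reading is that for-cause images from 32 of 36 study weeks are lost (32/36 = 89%). That is a share of calendar time in which an image could later be superseded. It is not a share of images, findings or participants, and it is no measure of undercounting.

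For MRI, no scheduled post-baseline examination is described. If the rule is applied per modality, only a later MRI can displace a for-cause MRI.

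The laboratory comparison is also only partial. The laboratory section has by-visit summaries besides its shift tables, and the imaging table is a by-visit summary. The SAP is therefore not in contradiction with itself; it lacks for imaging the extreme-value companion that it gives to other safety data.

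Finally, a worst-ever count gives more chances of a positive to participants who are imaged more often, so it mixes lesion frequency with imaging frequency. This is a fair objection to replacing the by-visit table, but not to adding a row beside it. Section 4.2.6 permits additional safety summaries, but that permission does not specify this one in advance.

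**Conclusion.** The point holds for the X-ray and MRI summary table in section 4.2.6.12. As written, an abnormal for-cause image followed by a later image is not counted there unless the finding still shows. Because last is not defined per joint or modality, a literal programmer could let an image of one joint or type displace an abnormal image of another. Relative to any post-baseline abnormality, the table can only be equal or too low, and its Week 32 label can cover images taken at other times.

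The size is unknown and cannot be derived from the SAP. No efficacy result is affected, nor are the adjudicated-event, special-interest or joint-replacement tables. The conclusion assumes that section 4.2.6.12 uses the visit mapping of section 3.1.8, which its reference to protocol-defined visits implies, and that some participants have more than one post-baseline image, which section 3.6.10 provides for.

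**What to change.** In section 3.1.8, state that the last-image rule applies per joint and per modality.

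In section 4.2.6.12:

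- Show the scheduled Week 32 X-ray as its own row, using only that film.
- Add a row for participants with any (worst) post-baseline abnormal finding across scheduled and for-cause images up to end of study.
- Show the number of participants with for-cause imaging per arm.

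The programming cost is small, since all assessable images are already to be listed. The drawback is that the any-abnormality row depends partly on how often participants are imaged. It should be read beside the scheduled Week 32 row and the for-cause imaging counts, not on its own.
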